### 7.3.5 BlueJeans Platform Description

For the mystery shopper debriefing sessions that occur over video chat, the BlueJeans platform will be used. BlueJeans is compatible with PCs, Macs, and any device with a web browser, including tablets and smartphones. Unlike other video-chat platforms (e.g. Skype), BlueJeans is HIPAA-compliant. BlueJeans includes the following functions to protect users:

*Media handling and encryption.* In WebEx, Vidyo, Tandberg, and Polycom architectures, media is sent to a server (also called a video relay or MCU). Although encryption is applied from the user's computer to these servers, the servers still have full access to the user's media. In contrast, Blue Jeans does not record or store your information; they simply encrypt and transmit it. Blue Jeans Network does not store any video conference content, in any format. This security infrastructure means Blue Jeans has no control over the content shared via video conference. BlueJeans supports standards-based encryption (AES-128) for video conferencing. .

*Infrastructure and network security.* BlueJeans employs a wide range of security management. This includes network firewalls throughout the infrastructure to create security zones for different applications and services. BlueJeans also deploys proxy servers that terminate all third party/customer traffic at a proxy layer. All web traffic passes through industry-leading load balancers to protect against a suite of application attack vectors. Beyond the firewall, proxy servers, and load balancers, BlueJeans also periodically scans for network, port, and application-level vulnerabilities. Vulnerability scans are conducted by a leading third party SaaS provider, in addition to some special-purpose, in-house scanning tools. Furthermore, all of the third party applications and operating system software is checked for security advisories and is patched periodically. Routers, firewalls, load balancers, and proxy application servers are all configured to mitigate numerous types of DOS attacks. BlueJeans also engages with third party consultants to perform penetration testing of the service.

*No-install client.* Video conferencing software clients tend to be large and to leave a big footprint on the user's system. Almost all of them require administrator permissions to install. Once the client software gains administrator permissions, they can severely compromise computer security. BlueJeans offers browser-based conferencing system that does not require administrator permissions or installation.

BlueJeans offers the HIPAA-required Business Associate Agreement (BAA) where BlueJeans agrees to be responsible for keeping all patient information secure and to immediately report any breach of personal health information. In this study, University of Pennsylvania will maintain a BAA with BlueJeans, and this will be extended to cover the proposed activities. The BlueJeans sessions will include identifying information (e.g., images of the participant, voice recordings). All identifying information will be stripped from the recorded BlueJeans sessions before they are sent to the analysis team for content analysis.

## 7.4 Data Submission

### 7.4.1 CRFs

Although the iTech projects will involve substantial online follow-up, we will use CRFs to collect data on study milestones such as completion or discontinuation, protocol deviations, any social impact reported by participants, and adverse events (AEs). During study conduct, the SRVs will complete electronic CRFs, transmit to the AC using iDataFAX, a leading multi-site database environment for HIV RCT. DataFAX can receive and transcribe CRF data via fax and scan, or allow for direct data entry. It provides for monitoring form completion and data-quality, and a system for data querying and resolution with SRVs, while maintaining an audit trail. The AC uses DataFAX for MSM studies and RCTs and maintains a secure DataFAX Linux server at Emory.

### 7.4.2 Audiotape Data

Interviews with agency directors will be audio-recorded to allow for verbatim transcription of the interview, and checked for accuracy and completion. We will format all transcripts and import them into qualitative data analysis software. Data analysis will be primarily conducted by Drs. [name] and [name], and will also involve ATN members from the Analytic Core and Get Connect study team members when appropriate. After one year when the study is over, audio recordings will be destroyed.

### 7.4.3 CASI Data Transmission

Only authorized users will be able to access and open the survey through SurveyGizmo. To ensure data privacy, as soon as data is entered (in real-time), it will be encrypted during transmission to the AC using Secure Socket Layer (SSL) technology. The data will routinely be downloaded and stored in a secure database on an AC server within the AC data center.

### 7.4.4 Retention data

The study will use a HIPAA-compliant web-based platform entitled Study Management and Retention Toolkit (SMART), which is a SaaS (Software as a Service) based mobile application aiding studies with various aspects of participant recruitment, study implementation, and retention. The application has the ability to securely manage participant information across multiple studies and customers simultaneously, stratifying participant information by study and site. SMART includes an admin web portal and a participant facing mobile app (optional), which allows for secure messaging, study calendar management, self-scheduling by participants, secure photo uploads, and longitudinal tracking of participants from screening to study completion. The ability to designate specific roles to all SMART users allows for greater control around permissions and accessibility to participant information. Users can even be limited to a reporting only role, which allows for study oversight through real time aggregate reporting, but no access to PHI. SMART is a licensed service of the Center for AIDS Research (CFAR) at Emory University, Prevention Science Core. Utilization of the mobile app is optional and the admin web portal will fully function without it.

As a backup in the event that the web portal is down or SRVs cannot access it, the study will use a non-web-based version of SMART, which maintains all contacts and scheduling records into a dynamic database that can be queried, in order to facilitate participant retention and communication. SMART was developed by the Emory Tech Core team in a Microsoft Access and SQL (Structured Query Language) Server environment. All data will be stored on an SQL server in the "trusted zone" (HIPAA compliant) area of the Emory Rollins School of Public Health computing service. Access to this database requires user permissions, connection to the Emory network via a VPN, and two-factor authentication using Duo. Daily backups of the entire database are performed. In the event that there are technical difficulties with site access to the Emory SQL Server environment, the SMART back-end database file will be stored in a user-restricted folder on the Emory network (the "T: drive research share", which requires secure Emory VPN access and two-factor authentication. If there are difficulties with the VPN connection to the Emory network, then a password-protected Microsoft Excel version of SMART will be made available to SRV users in their site-specific (and user-restricted) Box folder. These back-up systems provide a comparable level of data security and will be limited to the same number of users as the primary management system. These back-up systems are necessary for ensuring secure maintenance of study data, and secure, uninterrupted access to study data.

#### **7.5 Data Quality Assurance**

Investigators receiving federal funding must adhere to the Code of Federal Regulations (CFR) to protect research participants and produce reliable study information. The iTech AC will monitor data entry and will have an internal quality assurance plan that will identify problems and correct errors in research study records.

#### **7.6 Role of Data Management**

The AC will provide instructions concerning the recording of study data on the CRFs, and entry of the data into the AC data management systems.

#### **7.7 Study Site Monitoring and Record Availability**

Site monitors from the MC and AC will visit participating study sites to review a selected portion of the individual participant records, including assent/consent forms, CRFs, and supporting source documentation to ensure the protection of study participants, compliance with the protocol, and accuracy and completeness of records. Regulatory files, as required, will also be inspected to ensure that regulatory requirements are being followed.

The site investigator will make study documents (e.g., assent/consent forms, case report forms) and pertinent hospital or clinic records readily available for inspection by the local IRB, the central IRB, the site monitors, the NICHD, the Office for Human Research Protections (OHRP), or the sponsor's designee for confirmation of the study data.

## **8.0 PARTICIPANT MANAGEMENT**

### **8.1 Tracking RCT Participants for Follow-up**

For the primary objective, participants will be emailed once the appropriate time period has elapsed (30 days after baseline, 2 months after the 1-month survey, and 3 months after that for all other follow-up surveys), to notify them that a new follow-up survey is available. Multiple contact methods will be used for participants who do not complete their follow-up surveys after being emailed (e.g., phone calls, alternative email addresses, text messages, Facebook/other social media accounts). Participants will be asked whether or not messages can be left for any phone numbers they provide. They will be informed that messages will not contain any information regarding the nature of the project.

### **8.2 Compensation**

For the primary objective, participants will be able to earn up to \$155 total: Baseline survey = \$20, FU1 (Month 1) = \$20, FU2 (Month 3) = \$25, FU3 (Month 6) = \$30, FU4 (Month 9) = \$30, FU5 (Month 12) = \$30. This is the standard compensation used by both Drs. [name] and [name] in their ongoing YMSM studies, each of which has maintained >90% retention. We back-loaded the FU incentives to encourage completion of all data collection time points and reduce participant attrition over time. To receive the month one survey incentive, participants must complete the survey within 30 days of receiving the email with their unique survey link. To receive their month three, six, nine, and twelve survey incentives, participants must complete the surveys within 45 days of receiving each email with their unique survey link.

For the secondary objective, participants will earn \$100 for the training session and \$50 per site visit. The site visit includes an appointment at the designated site, completion of the post-visit survey, and a debriefing session with a member of the study team.

For the tertiary objective, site directors will not be compensated for the qualitative interview.

### **8.3 Intervening on "Social Harms"**

All sites have specific policies governing the treatment of human participants. These policies specify that medical and psychological assistance will be available in the immediate environment in the event a participant should experience any adverse reactions resulting from study procedures.

While participants will be informed that they may refuse to answer any question at any time, responses or reactions to certain questions may indicate distress on the part of the participants. If at any time during the study, a participant divulges that he is at risk for harm, including but not limited to being abused or experiencing violence, if harm is suspected or likely, or if the participant states he is suicidal/homicidal, measures will be taken to ensure his or her safety. Reporting will be done as appropriate to the situation and the legal statutes, including reporting

to child protection agencies or other appropriate agencies and referrals will be provided to appropriate support, counseling, or treatment resources.

#### **8.4 Criteria for Premature Study Discontinuation**

The principal investigator has the authority to withdraw any participant at any time if it their opinion it would be in the best interest of the participant. The participant will be informed of this withdrawal and explained the rationale. Withdrawal will be documented in the study tracking system.

For the primary objective, participants will be prematurely discontinued from the study if any of the following occurs:

- 8.4.1 The participant withdraws consent/assent (see below);
- 8.4.2 The study is cancelled by the NIH (or iTech, or other administrative entity);
- 8.4.3 The study is cancelled for other administrative reasons;
- 8.4.4 The participant becomes incarcerated or placed in detention during the study
- 8.4.5 The participant reports an HIV positive diagnosis; or
- 8.4.6 Death of the participant.

For the secondary objective, participants will be prematurely discontinued from the study if any of the following occurs:

- 8.4.7 The participant withdraws consent (see below);
- 8.4.8 The participant is found to be dishonest about their site visits;
- 8.4.9 The study is cancelled by the NIH (or iTech, or other administrative entity);
- 8.4.10 The study is cancelled for other administrative reasons;
- 8.4.11 The participant becomes incarcerated or placed in detention during the study; or
- 8.4.12 Death of the participant.

For the tertiary objective, participants will be prematurely discontinued from the study if any of the following occurs:

- 8.4.13 The participant withdraws consent/assent (see below);
- 8.4.14 The study is cancelled by the NIH (or iTech, or other administrative entity);
- 8.4.15 The study is cancelled for other administrative reasons;
- 8.4.16 The participant becomes incarcerated or placed in detention during the study; or
- 8.4.17 Death of the participant.

Participants may end their participation in the study at any time. No further data collection will occur from the date the decision is made to permanently discontinue the subject from the study. Participants who experience distress during the survey can access our list of community referrals, which can be viewed on our study's website, or contact the research staff using the information provided to the participant within the consent/assent process. Any unexpected adverse events that meet the New Safety Information reporting criteria will be immediately reported to the UNC-CH IRB and the respective sites' IRBs if applicable. All study activities will halt pending UNC-CH IRB review and recommendations if necessary. If a participant withdraws from the research, all data collected in the interview will be immediately destroyed and will not be used in subsequent analysis.

For all objectives, if a participant withdraws or is removed from the study, the Get Connected Off Study Form will be completed.

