### 3.0 STUDY DESIGN

#### 3.1 Study Phases

In this four-year study, we will enroll 480 self-reported HIV-negative or sero-status unaware, sexually active YMSM (ages 15-24) across three sites and randomize them into the GC intervention condition or to an attention-control condition. Primary outcomes will include (1) use of HIV prevention services (HIV testing, STI testing) and PrEP awareness and willingness. As secondary outcomes, we will assess PrEP use, sexual risk behaviors, and the linkage and retention in care among newly diagnosed HIV+ cases. We will also examine changes in GC's theorized mechanisms of change, including YMSM's attitudes, norms, self-efficacy, and behavioral intentions to adopt HIV prevention services.

Control condition: Participants randomized to the control condition will have access to the site locator portion of the Get Connected website, which includes information on HIV prevention services. While the provision of a test locator is a form (albeit weak) of an intervention, we felt that withholding referrals to testing and care services would be unethical given YMSM's vulnerability to HIV and STIs. Furthermore, given the availability of search engines to locate HIV/STI testing sites, the test locator condition may be considered usual care. Nevertheless, by providing the testing site locator only, we will be able to test the effect of the GC intervention condition (i.e., user-tailored content focused on HIV/STI testing and PrEP referral and the linkage to high-quality agencies) against the usual care control condition.

Intervention condition: Using a consensus approach to conceptualize health behavior change, the model guiding GC synthesizes The Integrated Behavioral Model and Self-Determination Theory as the theoretical underpinnings of our intervention. These theories emphasize social cognitive factors that impact behavior change and have informed HIV interventions. Consistent with these theories, GC content follows motivational interviewing (MI) principles by focusing on resolving ambivalence about HIV prevention behaviors, increasing self-efficacy for change, and enhancing motivation moving toward action. The intervention was developed by customizing content based on YMSM's psychosocial and sexual

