## 5.4 Intervention/Investigation Procedures

### 5.4.1 Get Connected Intervention

Participants will complete a 30- to 45-minute baseline survey that includes questions on lifetime HIV testing history, lifetime STI testing history and knowledge about STIs, date of their most recent STI test (if known), and whether they were ever diagnosed with an STI. GC will use baseline survey data to select and deliver personalized, tailored content to YMSM assigned to the intervention. Furthermore, as part of the participant's baseline visit, study staff will collect contact information where participants may be reached for follow-up assessments. We will use best practices to retain participants (e.g., collecting participant's cell phone number, email address, Facebook, WhatsApp, and/or Skype username, and contact information for 2 peers who could help us contact them). Additional surveys will occur at 1, 3, 6, 9, and 12 months after intervention initiation, and can be completed online. These follow-up surveys will repeat many of the questions from the baseline survey and will also include additional questions on HIV and STI testing in each 3-month period, including test results. These surveys will be the same for participants in the control and intervention arms. For participants in the intervention arm, the GC WebApp will be retailored after each follow-up survey, based on any different information provided on key questions.

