### 6.1.2 On-study Evaluations/Measures

- *HIV Testing:* Follow-up surveys will repeat the HIV testing questions in each follow-up survey. The HIV testing outcome will be: the proportion of MSM tested for HIV two or more times at least 3 months apart in the 12-month follow-up period (“frequent tester”). As an additional analysis, we will also examine the proportions of participants who receive one HIV test.
  - Among self-reported newly diagnosed HIV+ cases, we will measure their linkage and engagement with appropriate medical care after initial diagnosis using criteria employed in prior ATN protocols with youth. We will define linkage as an HIV-related medical visit within 45 days of referral, and engagement as a second HIV-related medical visit within 16 weeks of initial visit. Onset of ART initiation, self-reported adherence to ART, and viral suppression are exploratory indicators, as we recognize that our follow-up period may not be a sufficient amount of time to see these changes.
- *STI Testing:* The STI testing outcome is defined as the proportion of YMSM tested for STIs at least once in the 12-month follow-up period. We will ask participants what STIs they have been tested for, the anatomic sites where they were tested, the date of their most recent STI test (if known), and whether a medical provider had diagnosed them with an STI. In the follow-up surveys, we will ask participants whether they had been tested for STIs in the past 3 months (for the 1-month follow-up survey, we ask about the past 30 days). If STI testing is reported, we will ask participants to indicate what tests they received, and whether they were diagnosed with an STI by a medical provider.
- *PrEP Use:* At each follow-up assessment, PrEP-eligible HIV-negative YMSM (per CDC guidelines) will be asked whether they have begun using PrEP. We will also ascertain if a provider recommended PrEP and/or were offered a prescription for PrEP.
 

*Site Evaluations:* Across both trial arms, YMSM who report testing in the prior 3 months will complete self-evaluation forms of their testing experiences to assess comfort, quality, and concerns after visiting a site for HIV/STI testing and PrEP prevention services. The assessment form is the same form used by the mystery shoppers. We will use these data to update the WebApp and to send aggregate data of YMSM's satisfaction with services to agencies biannually.

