### 6.1.3 Premature Discontinuation/Off-Study Evaluations/Measures

RCT participants who request voluntary withdrawal and discontinue study participation after the Baseline survey but prior to the completion of the final survey at 12 months will be contacted by SRV staff in an attempt to understand the reason(s) for the participant's withdrawal and to potentially improve the service experience of the study and refine procedures.

Participants who are prematurely discontinued by a study PI or SRV staff will not be allowed to re-enroll into the study. Reason(s) for study discontinuation will be recorded through a CRF.

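### Reporting an HIV-positive diagnosis ends data collection, so the secondary outcome of linkage and engagement in care after that report is cut short

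*Combined protocol and SAP*

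**What the plan says.** Section 8.4 requires early discontinuation of a randomised participant under several conditions. Item 8.4.5 is "The participant reports an HIV positive diagnosis; or". The same section adds: "No further data collection will occur from the date the decision is made to permanently discontinue the subject from the study". Section 6.1.3 closes the way back: "Participants who are prematurely discontinued by a study PI or SRV staff will not be allowed to re-enroll into the study".

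Section 3.1 lists among the secondary outcomes "the linkage and retention in care among newly diagnosed HIV+ cases". Section 6.1.2 says how it is measured: "Among self-reported newly diagnosed HIV+ cases, we will measure their linkage and engagement". The definitions follow: "We will define linkage as an HIV-related medical visit within 45 days of referral, and engagement as a second HIV-related medical visit within 16 weeks", the latter counted from the first such visit. ART initiation, adherence and viral suppression are added as exploratory indicators, with a caution that follow-up may be too short to see them change.

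The data come from participant surveys. Section 5.4.1 states "Additional surveys will occur at 1, 3, 6, 9, and 12 months after intervention initiation", with "additional questions on HIV and STI testing in each 3-month period, including test results".

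**The concern.** The self-report that makes a participant a case for this outcome is also the event that ends his data collection. Section 6.1.2 expects follow-up after diagnosis, and Section 8.4 takes it away. The documents contain no exemption for newly diagnosed participants, no linkage to medical records, and no rule for a care window still open at removal. The off-study contact in Section 6.1.3 concerns voluntary withdrawal and asks for reasons, not care visits.

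Two things are at stake. Site staff cannot follow both sections, so sites may handle new diagnoses differently. And a case with no recorded visit often cannot be told apart from one removed before the window closed. Section 10.4 offers complete-case analysis and last value carried forward as general options without saying which applies here, and the choice can move the estimate in either direction.

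**Working it through.** The plan gives no figure for how much of each window would be observed, so there is none to reproduce. The contradiction is in the text; the arithmetic only sizes it.

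**Inputs from the documents**
- Surveys at months 1, 3, 6, 9 and 12 (Section 5.4.1). With a month of 365.25/12 days, the gaps are 30.4, 60.9, 91.3, 91.3 and 91.3 days.
- Linkage window 45 days; engagement window 16 weeks = 112 days (Section 6.1.2).
- Visit windows of ±1 month (Section 2.4); projected attrition of 20% (Section 3.1).

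**Assumptions not in the documents**
- Diagnosis dates are uniform over 12 months, and referral is on the day of diagnosis.
- The diagnosis is reported at the next completed survey, and the discontinuation decision falls on that day.
- The survey can capture visits back to the diagnosis.

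**Share of windows fully observed, surveys on schedule**

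For a window of w days, share = Σ max(0, gap − w) / 365.25.
- w = 45: (0 + 15.9 + 3 × 46.3)/365.25 = 42.4%.
- w = 59 (referral 14 days after diagnosis): (0 + 1.9 + 3 × 32.3)/365.25 = 27.1%.
- w = 112: 0%. The longest gap is 91.3 days, so this holds whatever the distribution of diagnosis dates.

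**Late and missed surveys** (simulation of 1,000,000 diagnoses; all diagnoses in the denominator)

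| Scenario | 45 days | 112 days from diagnosis | 112 days from a first visit uniform on days 0–45 |
|---|---|---|---|
| On schedule | 42% | 0% | 0% |
| Completion uniform over ±1 month | 44% | 2.4% | about 0.6% |
| 20% of surveys missed at random | 48% | 9.8% | 6.8% |
| Both | 49% | 11.3% | 7.3% |

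If each survey is instead timed from the previous late one, which is one reading of Section 8.1, the shares rise to 53–63% and 4.5–13%, and to 60% and 20% when 20% of surveys are also missed. Those schedules overrun the month-12 window.

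**Effect on the linkage estimate** (on schedule; illustrative true linkage 60%, first visits uniform over days 0–45)
- For a linked case, the chance that the visit precedes the reporting survey is the 42.4% whose window has closed plus the partial windows: [30.4²/90 + 4 × 45²/90]/365.25 = (10.3 + 90)/365.25 = 27.5%. The total is 69.9%.
- Open windows counted as failures: 0.60 × 69.9% = 41.9%.
- Status known (visit seen, or 45 days elapsed without one): 41.9% + 0.40 × 42.4% = 58.9% of cases. Linkage among these is 41.9/58.9 = 71%.
- Kaplan-Meier at day 45, censored at the reporting survey: 60.0% in simulation.
- With true linkage of 80%, the three results are 56%, 87% and 80%.

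Censoring cannot recover the 16-week engagement proportion on schedule: no follow-up reaches 112 days.

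**Number of cases.** The documents give no incidence. At an assumed 1–5% of 480 there are 4.8–24 cases; × 42.4% = about 2–10 with the 45-day window fully observed.

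**How much is due to the discontinuation rule.** If collection ran to month 12 regardless, the complete shares would be (365.25 − 45)/365.25 = 88% and (365.25 − 112)/365.25 = 69%. This is a benchmark, not a proposed rule.

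**The case against.** The strongest reply accepts the contradiction and disputes its size and weight.

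- **More is known than 42% suggests.** A visit already recorded at the reporting survey settles linkage, so status is known for about 59% of cases at a true linkage of 60%. Second visits before the report also count towards engagement. This stands: 42% and 0% are shares of closed windows, not of usable records.
- **Some loss is unavoidable.** The 88% and 69% benchmarks show that month 12 cuts off some windows anyway. This stands, but the rest of the loss comes from item 8.4.5.
- **The bias depends on the analysis chosen.** If complete data means that the full 45-day window was seen, the estimate is 60%, unbiased under these assumptions. Section 10.4 does not assign last value carried forward to this outcome. Both points are correct. The plan does not choose, which is why the 42% and 71% are possible results rather than predictions.
- **The inputs are soft.** Treating the 20% attrition as permanent dropout reached by month 12 gives about 36% for the 45-day window and none for 112 days on schedule. Diagnoses in months 0–3 give 15.9/91.3 = 17%; months 3–12 give 46.3/91.3 = 51%. If recall stops at 3 months, no 112-day window is observed in any scenario. The percentages are therefore illustrative.
- **The outcome is minor.** Linkage appears in none of the Section 2.4 hypotheses, is not powered in Section 10.2, and would rest on few cases. This limits the consequence.

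None of these points supplies an exemption or another data source.

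**Conclusion.** The plan is wrong as written on this point: Section 8.4 cannot be followed together with Sections 3.1 and 6.1.2. That conclusion needs no modelling, nor does the finding that no 16-week window closes between consecutive surveys completed on schedule. The 42% for the 45-day window, and the reported linkage of 42% or 71% against a true 60%, rest on the assumptions listed and would move with the timing of diagnosis, referral, recall and dropout. The outcome is truncated rather than lost. The consequence is confined to a secondary outcome with few expected cases; the primary HIV-testing comparison is not touched by this point. It should be fixed, but it does not threaten the trial's main conclusion.

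**What to change.** Reconcile Section 8.4 with Sections 3.1 and 6.1.2. This review takes no position on which discontinuation rule is right. There are three ways to do it:

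1. The investigators clarify whether already scheduled data collection may continue after a reported diagnosis and, if so, what happens to the re-tailoring of the WebApp after each survey (Section 5.4.1). This needs a text change and, if collection continues, changes to consent wording, survey skip logic and the re-tailoring link in the intervention arm. Windows cut off by month 12 would remain incomplete.
2. Restate the outcome as care visits recorded by the survey that reports the diagnosis. Treat cases whose window was not fully observed as censored, not as failures or exclusions, and report engagement only as far as follow-up extends. This costs text edits only.
3. Remove linkage and engagement from the secondary outcomes. This also costs text edits only.
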